7.4 SUV Outcomes

Analysis set(s): Efficacy set

Same analyses as Primary outcome (Section 7.2) on aorta, carotid arteries.

8 Soluble and Cellular Biomarkers

Analysis set(s): Efficacy set, Supplementary analysis set 1.

- All change-from-baseline-to-week-24 outcomes described in Section 3.3 will be analyzed in the same manner as the Primary outcome (Section 7.2).
- Soluble biomarkers may be transformed for analyses on the \log_{10} scale and back transformed to fold change for interpretation and presentation, as appropriate.
- Missing data will be ignored; all analyses will be complete case including only participants with paired values of each given biomarker available.

[figure not shown]
8.1.1 Distribution Plot of Biomarkers by Visit Week

Analysis set(s): Efficacy set

Stratification: Overall, by statin-use

Grouped by: Baseline, Week 24, Change

- Figure: Jitter and boxplot of biomarkers at baseline and week 24 by treatment arms (with a 3rd group of boxplots showing the within-participant change)

9 Pharmacokinetic (PK) / Pharmacodynamic (PD) Outcomes

Analyses in this section are subject to change based on pending review of current literature of CVC and ART drug-drug interactions. Based on review of participant regimens, only bictegravir (BIC), dolutegravir (DTG), rilpivirine (RPV), tenofovir alafenamide (TAF), emtricitabine (FTC), and lamivudine (3TC) have exposure by at least 10 participants.

All PK outcomes are limited to participants in the CVC arm.

9.1.1 Descriptive Statistics of CVC Trough Estimates by ART Class

Analysis set(s): Complete case set (cenicriviroc arm only)
Grouped by: a) ART Class (INSTI, NNRTI, both); b) ART Agent

Table	CVC Trough Estimates by ART Class / Agent
Characteristic	Summary Statistic(s)
Participant-level average CVC trough concentration	Median (Q1, Q3), and P10, P90
CVC trough concentration by week	Median (Q1, Q3), and P10, P90

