POPULATION	Individuals living with HIV 
• ≥ 45 years of age• On stable non-nucleoside reverse transcriptase inhibitor (NNRTI)-based or unboosted integrase strand transfer inhibitor (INSTI)-based antiretroviral therapy (ART) regimen, defined as no within-class changes in ART regimen within 12 weeks prior to entry and no between-class changes for 24 weeks prior to entry• With suppressed HIV-1 RNA for ≥ 48 weeks prior to entry• With at least one of the following cardiovascular risk factors (current diagnosis or receiving treatment):
○ Clinical atherosclerotic disease○ Subclinical atherosclerotic disease○ Diabetes mellitus (DM) or prediabetes or impaired fasting glucose or insulin resistance○ Obesity or enlarged iliac waist circumference○ History of hypertension or blood pressure $\geq 130/80$ mmHg○ Elevated low-density lipoprotein (LDL) cholesterol○ Low high-density lipoprotein (HDL) cholesterol○ Smoking (any current tobacco smoking)

- Family history of premature coronary artery disease (CAD; first degree relative with CAD prior to age 55 for male relative and 65 for female relative)
- High sensitivity C-reactive protein (hsCRP) >2.0 mg/L

STRATIFICATION

Randomization will be stratified by current use of statins (defined as statin use within the past 90 days prior to study entry versus none) to ensure even distribution of statin use between the treatment arms.

REGIMEN

Participants will be randomized 2:1 to either the CVC arm (Arm A) or placebo for CVC arm (Arm B). CVC 150 mg or placebo for CVC by mouth once a day for at least 24 weeks will be added to the participants' pre-existing antiretroviral (ARV) regimens.

For participants who are on an efavirenz (EFV)-based regimen, dosing will be 300 mg once a day.

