Clinical drug-drug interaction studies have been performed by Allergan, plc, in healthy adult volunteers. To summarize, CVC exposure was increased when co-administered with protease inhibitors (ritonavir [RTV], darunavir/ritonavir [DRV/r], or atazanavir/ritonavir [ATV/r]). Although the PK profile of CVC in combination with cobicistat (COBI) has not been studied, it is assumed that there will be significant increase in CVC concentration when co-administered with regimens boosted with COBI since COBI is a potent CYP3A inhibitor. CVC exposure was decreased when co-administered with efavirenz (EFV) and dolutegravir (DTG), but not changed with tenofovir (TFV). Co-administration with CVC increased TFV and ATV/r exposure, and had no effect on Efv, DRV/r, or DTG exposure. For Efv specifically, there was a 23% reduction in CVC Cmax, a 43% reduction in AUC0-24, and a 48% reduction in Cmin with Efv co-administration, which is a large enough reduction in CVC exposure to warrant a CVC dosage adjustment when given with Efv. (See Cenicriviroc mesylate [CVC] Investigator's Brochure [IB], Version 8.0, dated 04/2022)

Based on these data, dosing will be 150 mg once a day for participants who are on an INSTI- or rilpivirine (RPV)-based regimen, and 300 mg once a day in the morning with food for participants who are on an Efv-based regimen at bedtime. Although co-administration with DTG reduced CVC exposure, the effect was modest and not

expected to be clinically significant (CVC IB, Version 8.0, dated 04/2022), and thus does not warrant dose adjustment. As RPV is not a potent inducer of CYP3A, we believe it is unlikely to accelerate metabolism of CVC; therefore, no dose adjustment is proposed for participants who may be receiving an RPV-based ART regimen. At this time, we will exclude participants who are on protease inhibitors or on regimens boosted by RTV or COBI.

Rationale for 2:1 Randomization

At study entry, participants will be randomized at a 2:1 ratio (CVC arm:placebo arm). The 2:1 allocation is chosen so that more participants may potentially benefit from CVC (as opposed to no benefit from placebo). This is felt to be particularly important in the context of a placebo controlled study in which participants are being asked to undergo multiple imaging studies. This approach will also give us more statistical power to assess within group changes for the CVC arm.

Rationale for Per-protocol Analyses

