In Study 108, there was a 2.55-fold increase in CVC Cmax, a 3.89-fold increase in AUC0-24, and a 5.75-fold increase in Cmin with ATV/r co-administration, which is comparable to the effect seen with co-administration of RTV alone in Study 104. In Study 112, there were modest effects of CVC on RTV Cmin (1.50-fold increase) and on atazanavir (ATV) Cmax (1.19-fold increase), AUC0-24 (1.33-fold increase), and Cmin (1.55-fold increase). There were no statistically significant effects of CVC on RTV Cmax or AUC0-24.

In Study 109, there was a 23% reduction in CVC Cmax, a 43% reduction in AUC0-24, and a 48% reduction in Cmin with EFV co-administration. CVC did not result in a meaningful change in plasma EFV exposure.

In Study 110, there was a 28% reduction in CVC Cmax, a 29% reduction in AUC0-24, and a 23% reduction in Cmin with DTG co-administration. CVC did not result in a meaningful change in plasma DTG exposure.

A summary of detailed results of these studies performed is shown in [Appendix I](#).

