11.3.2 Data Analysis

Pharmacokinetics

CVC Exposure: An average steady-state CVC trough concentration will be estimated by ART regimen (INSTI- or NNRTI-based ART) and compared between ART regimens and with historical data for CVC.

ART exposure: An average steady-state ART trough concentration will be estimated pre- and post-CVC/placebo for CVC dosing. Average steady state ART trough concentrations during CVC/placebo for CVC co-administration will be compared a) between those on CVC and those on placebo for CVC (inter-participant comparison) and b) with pre-CVC levels (intra-participant comparison).

Analyses will use time-adjusted linear mixed effect models with measured concentration log-transformed.

Pharmacodynamics

Correlation of CVC exposure to outcomes: A composite time-adjusted CVC exposure estimate over the 24-week study period will be obtained for each participant from the mixed effect modelling based on their measured concentrations at weeks 4, 8, 12, and 24. Associations of these empirical Bayes estimates and the following arterial inflammation outcomes measured will be estimated via Spearman's rank-based correlation.

- Change in most diseased vessel TBR from baseline to week 24
- Change in aortic TBR from baseline to week 24
- Change in carotid artery TBR from baseline to week 24
- Week 24 aortic TBR
- Week 24 carotid artery TBR

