Noteworthy Findings: In Group 1, co-administration of EFV 600 mg with CVC 200 mg daily for 10 days during Period 2 resulted in a significant decrease in CVC exposure compared to CVC alone, with Cmax, Cmin, and AUC0–24 being 23%, 48%, and 43% lower, respectively, for EFV + CVC co-administration compared to CVC alone. Dose adjustment of CVC to 400 mg daily in Period 3 offset the drug interacting effect of EFV 600 mg co-administration with CVC; for Cmax, Cmin, and AUC0–24, the ratios of the LS geometric means (90% CI) were 1.23 (1.12, 1.35), 0.85 (0.71, 1.01), and 0.98 (0.85, 1.12), respectively (i.e., with the 90% CIs including 1.00 for Cmin, and AUC0–24 and within the 0.80–1.25 “no-effect” range for AUC0–τ and within the 0.70–1.43 “equivalence” range for Cmax and Cmin). In Group 2, plasma EFV exposure remained essentially unchanged in the presence of CVC 400 mg daily.					

Study Number/Phase	Study Title	Participant Description	Dose & Administration	CVC Formulation	Endpoints
Allergan Study 652-1-110 Phase 1	A Phase 1, multiple-dose, open-label, crossover study in healthy participants to assess the effect of DTG on the PK of CVC and the effect of CVC on the PK of DTG and on a single dose of midazolam	40 healthy participants (20 in Group 1 and 20 in Group 2)	
Group 1:
 
Period 1: Single dose of midazolam 5 mg po on Day -1 and Day 9 + CVC 150 mg QD po after a standardized breakfast × 10 days (Days 1 to 10)
 
Period 2: CVC 150 mg QD po + DTG 50 mg po QD after a standardized breakfast × 10 days
 
Group 2:
 
Period 1: DTG 50 mg QD po after a standardized breakfast × 10 days
 
Period 2: DTG 50 mg QD po + CVC 150 mg QD po after a standardized breakfast × 10 days
	DP7_150 formulation, manufactured by QS Pharma	
 1. Plasma PK of CVC (Group 1) 2. Plasma PK of DTG administered with and without CVC 3. PK of midazolam and α-hydroxy midazolam 4. Safety and tolerability

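### The NNRTI class summary and contrast of CVC troughs pool efavirenz users on 300 mg with everyone else on 150 mg, so any efavirenz users mix the ART effect with a dose difference

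*SAP*

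**What the plan says.** The exploratory pharmacology objective (Protocol 1.4.7a and 11.1.1; SAP 2.3.3, objective 6) is to learn how INSTI- and NNRTI-based ART affect CVC troughs and to compare the troughs across regimens.

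The Protocol schema sets the dose by regimen: "For participants who are on an efavirenz (EFV)-based regimen, dosing will be 300 mg once a day". Protocol 2.1 adds that "dosing will be 150 mg once a day for participants who are on an INSTI- or rilpivirine (RPV)-based regimen", and Table 5.1.1-1 puts every regimen without EFV on 150 mg. The reason given in Protocol 2.1 is the interaction itself. EFV produced "a 48% reduction in Cmin with EFV co-administration" among other reductions, judged a "large enough reduction in CVC exposure to warrant a CVC dosage adjustment".

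For the analysis, Protocol 11.3.2 states: "An average steady-state CVC trough concentration will be estimated by ART regimen (INSTI- or NNRTI-based ART) and compared between ART regimens", and also plans a comparison with historical CVC data. The models it names are linear mixed models on log concentration, adjusted for time. SAP 9.1.1 gives medians, quartiles and 10th and 90th percentiles in the CVC arm, "Grouped by: a) ART Class (INSTI, NNRTI, both); b) ART Agent". No PK section of either document mentions a dose term, a dose split or dose normalisation.

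The introduction to SAP section 9 lists the agents taken by at least 10 participants. Rilpivirine is the only NNRTI on the list. The same text calls the PK analyses provisional, pending a literature review.

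**The concern.** Dose is completely tied to EFV use: every EFV user is assigned 300 mg and nobody else is. An NNRTI class average that includes EFV users therefore combines three things: any rilpivirine effect at 150 mg, the EFV interaction, and a doubled CVC dose chosen to offset that interaction. The last two pull in opposite directions.

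Read as the effect of NNRTI-based ART on CVC exposure, such an average would understate the EFV interaction and would not represent rilpivirine either. Comparing the pooled NNRTI figure with historical data raises the same question, because the plan does not say at which dose the historical data were obtained.

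**Working it through.** **Inputs.** All ratios are for CVC Cmin in Study 652-1-109 (Protocol 2.1 and Appendix I).
- Equal CVC dose with EFV: 48% lower, so the ratio is 1 − 0.48 = 0.52.
- Doubled CVC dose with EFV (400 mg against 200 mg): 0.85, 90% CI 0.71 to 1.01. Appendix I summarises this as "Dose adjustment of CVC to 400 mg daily in Period 3 offset the drug interacting effect of EFV 600 mg co-administration with CVC".
- EFV users: 0 to 9, because EFV is missing from the SAP list of agents with at least 10 users.
- Rilpivirine users: at least 10, from the same list.

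**Check of the stated figures.** The geometric midpoint of each 90% CI should return the stated ratio.
- Cmin: √(0.71 × 1.01) = 0.847, stated 0.85.
- Cmax: √(1.12 × 1.35) = 1.230, stated 1.23.
- AUC0–24: √(0.85 × 1.12) = 0.976, stated 0.98.

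All three agree.

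**Is trough proportional to dose?** Proportionality would give 2 × 0.52 = 1.04 at the doubled dose. The observed value is 0.85, and 1.04 lies just above the upper limit of 1.01. Halving the doubled-dose result gives 0.85 / 2 = 0.425, not the 0.52 measured at equal dose. Dose-normalised troughs would therefore not recover the equal-dose effect on these data.

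**Effect on the class figure.** Let f be the EFV share of the NNRTI group. Assume that rilpivirine has no effect (ratio 1), that no other NNRTI is used, and that the Study 109 ratios carry over to 150 and 300 mg. Relative to a no-interaction reference at 150 mg, the class geometric mean ratio is 0.85^f as dosed and 0.52^f at equal dose.

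| Rilpivirine users | EFV users | f | As dosed | Equal dose |
|---|---|---|---|---|
| 10 | 0 | 0.00 | 1.00 | 1.00 |
| 10 | 1 | 0.09 | 0.99 | 0.94 |
| 10 | 3 | 0.23 | 0.96 | 0.86 |
| 10 | 5 | 0.33 | 0.95 | 0.80 |
| 10 | 9 | 0.47 | 0.93 | 0.73 |
| 30 | 3 | 0.09 | 0.99 | 0.94 |
| 30 | 9 | 0.23 | 0.96 | 0.86 |

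For example, with 9 of 19, 0.85^0.474 = 0.926 and 0.52^0.474 = 0.734. The as-dosed value would be 0.71^0.474 = 0.85 at the lower confidence limit and 1.01^0.474 = 1.00 at the upper. Among 150 mg users alone the ratio is 1.00 in every row, by the rilpivirine assumption.

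**INSTI reference.** INSTI users need not be free of interaction: Study 110 found CVC Cmin 23% lower with dolutegravir. That would change the reference for both columns by the same factor. The gap between the columns, (0.85 / 0.52)^f, would not change. It is at most 1.635^0.474 = 1.26 in this table.

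**The case against.** Several points on the other side stand.

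- The grouping line in SAP 9.1.1 also lists individual agents. That table separates EFV from rilpivirine, and rilpivirine against INSTI is a dose-matched contrast at 150 mg. What the table lacks is a dose label.
- SAP 9.1.1 is descriptive and contains no test. The class comparison is only in Protocol 11.3.2.
- There may be no EFV users at all. The count of at least 10 in SAP section 9 is not stated to be for the CVC arm, so the number of EFV users in that arm may be smaller still. The 9-of-19 case pairs the largest EFV count the text allows with the smallest rilpivirine count.
- Protocol 11.2 mentions the EFV dosage adjustment and then gives the aim as describing CVC PK in people on these regimens. That allows a trough-as-dosed reading, under which comparing regimens at their assigned doses is the question intended. Neither document says so, and the objective's wording about the impact of ART points the other way, so the plan should state which is meant.
- The objective is exploratory, section 9 is provisional, and SAP 1.1 promises an implementation plan with fuller table outlines.

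Three stronger readings are tempting, and the documents do not support them. A reader might infer that the NNRTI contrast cannot show any ART effect. That does not follow, because rilpivirine users are on the common dose and EFV users are few. A reader might infer a collapse in power. The documents give no INSTI count, EFV count or between-person SD for troughs, so any power figure would rest on invented inputs. A reader might infer that the historical comparison is with 150 mg data. Protocol 11.3.2 names no dose, and Appendix I itself contains dose-adjusted EFV data.

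**Conclusion.** The point holds in a limited form. The class rows in SAP 9.1.1 and the class comparison in Protocol 11.3.2 take no account of dose, and dose is aliased with EFV use. Any EFV users in the CVC arm would therefore confound the NNRTI summary and contrast.

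The size depends on the EFV share. It runs from nil with no EFV users to a class ratio of 0.93 as dosed, against 0.73 at equal dose, in the extreme case. It is small when EFV users are few relative to rilpivirine users. These figures rest on the Study 109 ratios, which come from healthy adults given 200 and 400 mg of another formulation after dinner. They also assume no rilpivirine effect and no other NNRTI.

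Severity is low. No primary or secondary conclusion is affected, and nothing here bears on which dose is right.

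**What to change.** In SAP 9.1.1, and in the SAP's implementation of the Protocol 11.3.2 comparison:
- Limit the class summary and class contrast to participants on 150 mg.
- Show EFV users as a separate row labelled with their 300 mg dose and described as trough as dosed. Add the assigned dose to the by-agent table.
- Match any comparison with historical CVC data on dose, and state the dose used.

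A dose covariate is not a substitute: dose and EFV use coincide exactly, so a model cannot separate them. Dose normalisation should not be relied on either, because Study 109 does not show proportional troughs.

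The cost is one filter, one label and a few lines of SAP text, with no new data. The NNRTI class row loses at most 9 participants and no longer speaks to EFV. That is a real limit, but not one the fix creates: no participant is assigned EFV with 150 mg, so this trial cannot estimate the EFV interaction at equal dose under any analysis.

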9.1.2 Change in ART Trough Estimates

Analysis set(s): Complete case set
Grouped by: Specific ART Bictegravir, Dolutegravir, Rilpivirine
Stratification: None
Analysis method: paired t-test of pre-study treatment and participant-level average post-study treatment ART trough estimates with null hypothesis of no difference between pre- and post- study measures.

Table	Columns for each group: Pre, Post, Change	
Characteristic	Pre-, Post- Treatment Statistic(s)	Change Statistic
Average <DRUG> trough concentration	Mean (st.dev.), Median (Q1, Q3), and P10, P90	Mean, 95% confidence interval, p-value

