6.3.10 Pharmacokinetic Studies

At each visit indicated in [section 6.1](#), a single PK sample will be drawn and stored.

Participants should be stable on ART for at least 10 days (i.e., no ART regimen change for 10 days) prior to PK draws. The ART dose prior to the PK evaluations should be given as close to 12 hours prior to the PK evaluation as is feasible. Blood should be drawn before the morning dose of CVC/CVC placebo (as applicable) and ART. In the case where a morning CVC/CVC placebo or ART dose is taken prior to the trough measurements or if any of the four preceding doses have been missed, the PK sampling should be rescheduled during the same week, if possible. If this is not possible, contact the A5415 CMC ([contact]) for guidance. Dates and times of the last four doses of ART and CVC will be recorded.

For processing and shipping instructions, refer to the A5415 LPC. Refer to [section 11.0](#) for assay details.

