11.3 Primary and Secondary Data, Modeling, and Data Analysis

11.3.1 Outcome Measures

Blood for PK sampling will be collected at select study visits, and before the morning dose of CVC/placebo, as per protocol for CVC and ART. Trough ART levels will be determined for all participants at pre-entry and weeks 4, 8, 12, and 24. For those randomized to active drug, trough levels for CVC will be determined at weeks 4, 8, 12, and 24.

Only drug concentration levels determined from samples obtained at steady state (no missed doses within the preceding 4 days) and no more than 14 hours post last EFV-based ART or 26 hours post last non-EFV based ART and CVC/placebo for CVC dose will be used in analyses.

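### SAP 9.1.2 as written tests ART troughs with a paired t-test on averages, not the Protocol's time-adjusted log-scale mixed model; Section 9 also ties the PK set to paired PET/CT scans and drops the CVC-versus-placebo comparison without a stated reason (minor)

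*SAP*

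**What the plan says.** **Protocol.** Section 11.3.1 covers both arms: "Trough ART levels will be determined for all participants at pre-entry and weeks 4, 8, 12, and 24". Its data rule works sample by sample: steady state, and drawn "no more than 14 hours post last EFV-based ART or 26 hours post last non-EFV based ART". Section 11.3.2 plans two comparisons of ART troughs. One is "between those on CVC and those on placebo for CVC (inter-participant comparison"; the other is "with pre-CVC levels (intra-participant comparison". On method it says: "Analyses will use time-adjusted linear mixed effect models with measured concentration log-transformed". Section 6.3.10 says the ART dose "should be given as close to 12 hours prior to the PK evaluation as is feasible", and adds: "Dates and times of the last four doses of ART and CVC will be recorded".

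**SAP.** Section 9.1.2 covers bictegravir, dolutegravir and rilpivirine and specifies a "paired t-test of pre-study treatment and participant-level average post-study treatment ART trough estimates", reported as a mean change with 95% CI and p-value. It mentions neither a log transform nor time since dose. Section 3.3 measures ART troughs in the CVC arm only, and the opening of Section 9 limits every PK outcome to that arm. Sections 9.1.1 and 9.1.2 name the complete-case set. Section 4.1.4 defines it as the efficacy set (at least 22 weeks on treatment, same ART drug class) with paired baseline and week 24 PET/CT data. Exploratory objective 6b in Section 2.3.3 still asks about CVC treatment against no treatment.

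**Reasons given.** SAP 1.2 cites budget for reducing the immunology samples. No reason is given for the PK changes. Section 9 is marked as provisional pending a literature review of interactions, and the note in 2.3.3 concerns which ARTs to study.

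**The concern.** The SAP keeps the within-participant comparison, which answers objective 6b in part because the pre-entry sample is taken off CVC. It departs from the Protocol in three ways.

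- **Model.** Concentrations are usually analysed as ratios, and a sample's level depends on when it was drawn. The Protocol aims for about 12 h after the ART dose but accepts up to 26 h for non-EFV regimens. A t-test on raw averages ignores recorded dose times and gives an absolute difference rather than a ratio.
- **Analysis set.** Neither 9.1.1 nor 9.1.2 uses imaging data. A missing week 24 scan says nothing about whether a week 4 trough is valid. Stopping treatment early, or changing ART class later, does not spoil samples already taken at steady state.
- **Comparator.** Without placebo-arm troughs, a before-after change cannot be separated from a change common to both arms. Random allocation is not used for this question.

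At stake are the precision and the labelling of an exploratory drug-interaction result. No primary, secondary or safety conclusion depends on it.

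**Working it through.** The documents give no sample size, power or variance for the PK analyses, so there is no planned figure to reproduce.

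**1. Samples lost to the analysis set.** Protocol 10.4 assumes 20% total loss for the imaging outcome. It assumes 15% for outcomes with no image scheduling or quality loss. The planned CVC arm is 62.

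- Imaging-specific: 62 × (0.20 − 0.15) = 3.1 participants.
- All causes: 62 × 0.20 = 12.4 participants.
- With 110 enrolled and an exact 2:1 split, the CVC arm is about 73, giving 73.3 × 0.05 = 3.7 and 73.3 × 0.20 = 14.7.

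The all-cause figure is an upper bound. Protocol 6.2.4 stops PK sampling after premature discontinuation, so some of these participants have no valid on-treatment sample.

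**2. Model comparison (simulation; every input is an assumption).** For participant i and sample j:

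log C = bᵢ − (ln 2 / half-life) × tᵢⱼ + ln(1.2) × postᵢⱼ + eᵢⱼ

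There is one pre and four post samples, the SD of b is 0.5, the SD of e is 0.3, and the true effect is 20%. Half-lives are 12, 24 and 45 h, with 6,000 trials per cell (95% simulation error about ±1.3 points). The time-adjusted analysis is a within-participant regression of log concentration on pre/post and time, standing in for the random-intercept mixed model. Power (%) at 20 users, for half-lives 12 / 24 / 45 h:

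| Sampling times | Raw paired t | Log paired t, no time term | Log, time-adjusted |
|---|---|---|---|
| Each sample independent over 12-26 h | 43 / 52 / 56 | 45 / 58 / 62 | 67 / 66 / 67 |
| Each sample within 22-26 h | 57 / 58 / 57 | 62 / 63 / 62 | 67 / 66 / 66 |
| Each participant near a usual time (13 or 24 h, ±1.5 h) | 55 / 58 / 58 | 63 / 64 / 64 | 67 / 68 / 68 |

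Allowing for simulation error, this is about 65-68% for the time-adjusted log model. The raw paired t-test has about 55-59% with fairly consistent times and 42-57% with independent times. At 10 users and consistent times the figures are about 37-39% against 30-33%.

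With consistent times, much of the gap comes from the log scale and from pooling residual variance; the time term adds little. The pooling gain assumes one common effect and independent residuals.

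**3. Between-arm contrast (no timing noise, same SD).** SD of a participant's change = 0.3 × √(1 + 1/4) = 0.335, and ln 1.2 = 0.182.

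- Before-after, 20 CVC users: SE = 0.335 / √20 = 0.075, ratio 0.182 / 0.075 = 2.43 on 19 df, power 64%.
- CVC versus placebo, 20 and 10 users: SE = 0.335 × √(1/20 + 1/10) = 0.130, ratio 1.40 on 28 df, power 27%.
- At 10 and 5 users: 34% and 15%.

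The SE ratio is √3 = 1.73. The randomized contrast removes a common change but is much less precise.

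**The case against.** **The SAP may intend the Protocol's method.** Protocol 11.3.2 itself asks for average steady-state troughs before and after. Protocol 11.4 mentions time adjustment only for CVC. SAP 9.1.2 speaks of trough estimates, which could be model-based, and SAP 1.1 leaves further detail to an implementation plan. SAP 9.1.3 still cites Protocol 11.3.2 for CVC exposure, so the mixed model has not been abandoned throughout. This stands as a reason for caution, but 9.1.2 as written names a paired t-test and nothing more.

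**The set may mean paired PK values.** SAP 8 uses complete case for paired values of the biomarker concerned. Section 9 could mean the same, and it spells the term without the hyphen used in 4.1.4. That is possible, but the only defined set of that name is the PET/CT one.

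**Harm is not shown.** Participants have stable ART for at least 48 weeks before entry and no regimen change for 10 days before a PK draw. A reader might infer that a shift common to both arms will produce a false CVC effect. Nothing in the documents suggests such a shift or its size; the before-after design only leaves it unchecked.

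**Stronger power claims fail.** A reader might take the gap of about 43% against 67% as the likely cost. It needs each participant's sampling time to vary independently over 12-26 h, which sits poorly with a target time and blood drawn before the morning dose. A reader might also use the TDF increase of 28-36% in Protocol 2.1 as the effect to detect. SAP 9.1.2 does not test TDF, and for dolutegravir the Protocol reports no meaningful change with CVC.

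**Conclusion.** The point holds as a minor one, in three parts.

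- **Model:** 9.1.2 as written is less efficient than the Protocol's model. The cost is roughly 8 to 12 percentage points of power at 20 users when sampling times are fairly consistent, and more if they are erratic. This rests on an assumed log SD of 0.3, a 20% effect, and half-lives of 12 to 45 h.
- **Analysis set:** on its only definition, the set discards valid samples from about 3 of 62 planned CVC participants for imaging reasons, and up to about 12 for all causes. A reader might infer biased estimates. That would follow only if retention were related to the change in ART trough, for which the documents give no evidence.
- **Comparator:** the CVC-versus-placebo comparison in Protocol 11.3.2 cannot be done under SAP 3.3 and 9, and no reason is stated. Because that contrast has low power, the loss concerns interpretation and agreement between the documents rather than precision.

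The objective is exploratory, Section 9 is provisional, and an implementation plan may supply part of what is missing.

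**What to change.** 1. **SAP 9.1.2, model.** Use the Protocol 11.3.2 linear mixed model of log concentration, with time since dose, a pre/post term and a participant random effect. Report geometric mean ratios with 95% CIs.
2. **SAP 9.1.1 and 9.1.2, analysis set.** Replace the complete-case set with all treated CVC participants who have samples meeting the steady-state and timing rule of Protocol 11.3.1. Keep the paired-scan set for 9.1.3 only, where TBR is the outcome.
3. **SAP 3.3 and 9, comparator.** Reconcile with Protocol 11.3 and give the reason for the arm limit. If placebo-arm ART samples are assayed, include that arm, report the between-arm contrast beside the before-after estimate, and note its low power. If they are not, label the 6b result an uncontrolled before-after estimate.

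The ratio format, the explicit pre/post term and participant random effect, and the PK set are proposals made here; Protocol 11.3.2 does not spell them out. Items 1 and 2 cost SAP wording and modest analysis work, since samples and dose times are already collected. They do not remove a change common to both arms; only placebo-arm data can. Item 3 costs assays, or otherwise one reconciling sentence and a label.
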